Developing an LC-MS/MS method for measurement of tacrolimus and creatinine concentration from finger-prick blood collected using the Mitra device

RESEARCH REFERENCE NUMBERS

IRAS Number: 340380

SPONSORS Number: Generated by the Sponsor. Enter if applicable

FUNDERS Number: Generated by the funder. Enter if applicable

VERSION NUMBER AND DATE: Version 0.1 (29-08-2024)

Statistical Analysis Plan

Hypothesis:

The LC-MS/MS method for the quantitation of creatinine and tacrolimus in finger-prick samples collected from the Mitra device will produce results that are not statistically different from whole blood venous samples.

Methodology

[figure not shown]
Patients attending the Nottingham renal clinic for routine therapeutic drug monitoring for Tacrolimus will be consented to have a venous blood sample and a corresponding finger-prick sample (collected using the Mitra device) collected for tacrolimus and creatinine analysis (please see flowchart below).

50 samples will be collected from consented patients. The tacrolimus levels from the venous blood samples will be measured using the routine LC-MS/MS method and creatinine will be measured using the Abbott enzymatic creatinine method. The capillary-finger-prick samples collected using the Mitra device will be analysed using the optimised LC-MS/MS methods for creatinine and tacrolimus.

[figure not shown]
The results from the venous blood samples will be reported following routine laboratory processes (direct transfer of results from laboratory LIMS system to the electronic patient record). These results will then be transferred onto a password-protected spreadsheet accessible only by the investigators of the study. All data will be depersonalised. No patient identifiers will be taken from the electronic patient record – only the sample number, tacrolimus result, and creatinine result will be required. The results from the Mitra-collect finger-prick samples will be transferred to the same password-protected spreadsheet accessible only by the investigators of the study. These results will not be transferred to any patient record.

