Results of the Mitra-device collected samples and venepuncture collected samples will be compared. The data collected will be analysed using the 'Analyse-It' statistics software and Bland-Altman and Passing-Bablok regression analyses will be completed to identify any statistical differences between the two LC-MS/MS methods. Research data (excluding patient details) will be stored in the Laboratory Quality Management System (Q-Pulse).

[figure not shown]
Participant recruitment

Mitra-collected samples

Venepuncture-collected samples

Method comparison

Results of the Mitra-device collected samples and venepuncture collected samples will be compared. The data collected will be analysed using the 'analyse-it' statistics software. Research data (excluding patient details) will be stored in the Laboratory Quality Management System (Q-Pulse).

Results

Please see Flowchart for details of participant flow.

Patients will be recruited and consented by the renal clinical team. Patient Information leaflets will be distributed to all volunteers and consent forms signed by the participants or parents/carers for paediatric patients. 50 patients will be included in the study and the results from the venous blood and capillary-finger prick samples compared.

The results from the venous blood samples will be processed and reported using the normal laboratory processes (electronic transfer of results from the laboratory LIMS system to the electronic patient record), ensuring there is no delay in receipt of routine results. As the results from the finger-prick blood samples collected using the Mitra device will not be reported there will be no change to tacrolimus dosing regimens based on these results. There are no anticipated adverse events expected.

Results of the Mitra-device collected samples and venepuncture collected samples will be compared. The data collected will be analysed using the 'Analyse-It' statistics software and Bland-Altman and Passing-Bablok regression analyses will be completed to identify any statistical differences between the two LC-MS/MS methods. Research data (excluding patient details) will be stored in the Laboratory Quality Management System (Q-Pulse).

Interpretation

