Results of the Mitra-device collected samples and venepuncture collected samples will be compared. The data collected will be analysed using the 'Analyse-It' statistics software and Bland-Altman and Passing-Bablok regression analyses will be completed to identify any statistical differences between the two LC-MS/MS methods. Research data (excluding patient details) will be stored in the Laboratory Quality Management System (Q-Pulse).

The statistical analysis of the results will be compared to those previously reported by the Wythenshawe Laboratory (Marshall et Al. 2020) who have also introduced a finger-prick capillary collection method for tacrolimus and creatinine. The outcome of this study will be disseminated to the renal clinical team. If no statistically significant difference is identified between the methodologies, it is anticipated that the Mitra-devices could be utilised for remote blood collection and samples sent to the laboratory via postal services for tacrolimus and creatinine measurement. This would reduce the number of outpatient appointments required for patients requiring therapeutic drug monitoring.

References

Marshall, D. J., Kim, J. J., Brand, S., Bryne, C., & Keevil, B. G. (2020). Assessment of tacrolimus and creatinine concentration collected using Mitra microsampling devices. *Annals of Clinical Biochemistry*, 57(5), 389-396

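### Does the SAP's outlook on remote and postal use overreach a comparison made in clinic attenders?

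*SAP*

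**What the plan says.** The Methodology section of the SAP sets the recruitment: "Patients attending the Nottingham renal clinic for routine therapeutic drug monitoring for Tacrolimus will be consented to have a venous blood sample", together with "a corresponding finger-prick sample (collected using the Mitra device) collected for tacrolimus and creatinine analysis". The Results section gives the size: "50 patients will be included in the study and the results from the venous blood and capillary-finger prick samples compared". The Hypothesis is that the Mitra method "will produce results that are not statistically different from whole blood venous samples".

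The Interpretation section then looks ahead: "If no statistically significant difference is identified between the methodologies, it is anticipated that the Mitra-devices could be utilised for remote blood collection". The sentence goes on to postal return ("samples sent to the laboratory via postal services for tacrolimus and creatinine measurement"), and the next one names the benefit: "This would reduce the number of outpatient appointments required for patients requiring therapeutic drug monitoring". The same section plans a comparison with published results from another laboratory that uses finger-prick collection, and says that the outcome will go to the renal clinical team.

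The readable text does not say who performs the finger-prick or how the device reaches the laboratory. It refers the reader to flowcharts for participant flow, and these are not reproduced in the text available for this review.

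**The concern.** The conclusion appears to outrun the data. Remote use adds two steps: a patient or carer takes the sample unsupervised, and the sample spends time in the post. Either could add bias or scatter to the tacrolimus or creatinine result. The described comparison pairs samples from people who attend clinic, and the only condition named for the remote outlook is the absence of a statistically significant difference.

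If no study sample goes through self-collection or transit, error from those steps cannot appear in the estimated bias or the limits of agreement. The named condition could then be met however large that error is. A larger sample of the same kind would not help. The clinical team could take the result as support for a use that was never tested.

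**Working it through.** The SAP states no SD, margin, significance level or power, so there is no figure of its own to reproduce. The check has two parts.

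**Reading the sections together**

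| Section | What it covers | Reaches remote or postal use? |
|---|---|---|
| Hypothesis | Mitra finger-prick against venous results | No |
| Methodology | Paired samples from clinic attenders; carriage of the device not described | Not stated either way |
| Results | 50 patients, paired comparison | Not stated either way |
| Interpretation | Possible later use, in tentative wording | Yes, as an expectation |

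The formal claim matches the described data. Only the forward-looking remark goes further. It names one condition but does not say that this condition is sufficient, or that no further validation would come first.

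**Illustrating the size**

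Only n = 50 comes from the SAP. The SD of paired percentage differences, the shift, the added scatter and the two-sided 5% level are assumptions.

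1. Half-width of the 95% confidence interval for mean bias = t(0.975; 49) × SD/√50, with t = 2.010 and √50 = 7.071.
   - SD 10%: 2.010 × 10/7.071 = 2.84 percentage points.
   - SD 15%: 4.26 points.
   - SD 20%: 5.68 points.
2. Chance that a paired t-test flags a 5% mean shift that is present in the samples, from the noncentral t distribution with noncentrality 5/SD × √50.
   - SD 10%: noncentrality 3.54, probability 0.934.
   - SD 15%: noncentrality 2.36, probability 0.637.
   - SD 20%: noncentrality 1.77, probability 0.410.
3. If the shift arises only in handling that no study sample undergoes, and there is no other bias, the flag rate is 0.05 for a shift of any size.
4. Limits of agreement in use = ±1.96 × √(10² + s²), where s is independent added scatter and the study SD is 10%.
   - s = 0: ±19.6%.
   - s = 5%: ±21.9%.
   - s = 10%: ±27.7%.

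Step 2 concerns a shift that the study would see, which is not the situation feared. Step 3 does describe that situation, but it is true by construction: an effect assumed absent from the data cannot be detected in them. Step 4 adds one assumed variance to another. The SAP has no acceptance limit against which to judge ±21.9% or ±27.7%. The t-test is itself a stand-in, because the SAP names Bland-Altman and Passing-Bablok analyses without specifying a test of mean bias.

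The arithmetic shows what could be missed if handling matters and is untested. It cannot show that either is so.

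**The case for a change.** The strongest case for a change is that the criticism is aimed at a sentence the SAP contains, not at stability work it omits. That sentence links one statistical result to a use that the described comparison does not represent. The published comparison has no criterion and is not tied to it. Even if evidence on self-collection and transit exists elsewhere, the sentence does not make it a condition. The document is at version 0.1, so an edit would be cheap.

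Part of this stands. On the readable text alone, agreement in clinic attenders does not establish performance for samples taken at home and posted, and a report of the study should not say that it does.

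The step from there to a defect in the plan fails. The remark is tentative and governs no analysis. The harm depends on how the samples are taken and carried, and the text neither confirms nor excludes self-collection or posting. Recruiting people at a clinic does not settle that. Collection procedure and transit stability commonly sit in a protocol or laboratory validation file, and the Methodology section's mention of optimised methods points to development work outside this document.

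A stronger criticism of the same sentence is that it treats non-significance as agreement without acceptance limits. With a true 5% bias, a non-significant result occurs about 7% of the time at an SD of 10% and 59% at an SD of 20% (1 − 0.934 and 1 − 0.410), so noisier results make the condition easier to meet. That is a separate matter. A caveat about remote use would not resolve it, and it should not lend weight to this point.

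**Conclusion.** No change is called for. The outlook in the Interpretation section is wider than the described comparison, but it is an expectation about later use; the Hypothesis and the named analyses stay within what paired samples can address. A qualifying sentence would leave the sampling, the analyses and the 50 patients as they are. It would also alter no patient's care within the study, because Mitra results are not reported and do not affect dosing.

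The documents support no estimate of size. The widening from ±19.6% to between ±21.9% and ±27.7% rests wholly on an assumed study SD of 10% and assumed added scatter of 5% to 10%. Analysts writing up the study can be expected to confine their conclusions to samples collected and handled as they were, and to point to whatever self-collection and transit evidence exists before remote use is considered.

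This conclusion assumes that the Interpretation sentence will not serve as an adoption rule, which its wording supports. It does not assume that the unseen flowcharts or protocol contain the stability evidence, only that an SAP may leave such material to them.
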